#### 9.1.2 **PRE-PROCEDURE MEDICATION MANAGEMENT**

After the ablation procedure, patients should receive either an antiplatelet agent (aspirin, clopidogrel, etc) or anticoagulant (warfarin, dabigatran, etc) for at least 1 week. Further decisions regarding the peri-procedural management of other cardiovascular (including anti-coagulant and anti-thrombotic agents) and non-cardiovascular medications should be as per clinical practice – but every effort should be made to maximize beta-blocker therapy, ACEI/ARB, and spironolactone therapy as per the guidelines.

[figure not shown]
#### 9.1.3 VT ABLATION PROCEDURAL DETAILS

- Patients will be brought to the electrophysiology laboratory in a fasting state
- General anesthesia/conscious sedation will be used according to operator preference
- Patients will undergo electrophysiology study and VT ablation as per standard practice
- Therapeutic anticoagulation will be administered with intravenous heparing with a target ACT of 300 seconds or greater.

#### 9.1.4 RENAL SYMPATHETIC ABLATION PROCEDURAL DETAILS

• In patients randomized to receive RSDN, the procedure will be performed after the VT ablation on therapeutic anticoagulation with intravenous heparin.

- Abdominal aortography will be performed to assess the renal arteries for the suitability of catheter-based renal denervation in all patients. For those patients in whom the angiogram demonstrates that the renal anatomy is inappropriate for the RSDN procedure (small renal arteries, extensive atherosclerosis, renal stenosis, etc), the patient will be excluded from the study as a screen failure. The patient's baseline information will be collected but no further follow-up required (beyond assessing for any adverse events related to the procedure). If the renal arteries are deemed suitable for RSDN, the patient will then undergo randomization.
- Randomization will be done by permuted-block randomization centrally and will be stratified by site. Allocation concealment shall be maintained at all sites by the use of a web-based central randomization scheme. The operating physician controlling the delivery of ablative energy will be aware of the outcome. This approach has been selected to minimize (1) study bias and (2) placebo effect. The randomization schema will be blocked by size for each site.
- After confirmation of eligibility, an irrigated radiofrequency ablation catheter will be introduced sequentially into each renal artery.
- The ablation catheter is placed within a long vascular sheath and advanced into the renal artery. The sheath is advanced over the catheter to engage the renal artery ostium and allow for contrast injection and visualization of the vessel during catheter manipulation.
- After completion of the measurement, no more than six radiofrequency ablation lesions separated both longitudinally and rotationally (a —spid pattern", see figure) will be placed per renal artery. The power will be started at 10 W and titrated to a maximum 20 W, as deemed appropriate by the impedance drop (goal 10% drop). Each lesion should be between 30-120 seconds in duration (no more than 120 seconds per lesion).

#### 9.1 **POST-PROCEDURE**

### 9.2.1 POST-PROCEDURE FOLLOW UP

- All patients will be monitored to verify vascular hemostasis prior to discharge from the hospital.
- All patients will receive either oral aspirin (81-325 mg QD) or clopidogrel (75 mg QD) or warfarin or dabigatran or rivaroxiban for at least 1 week upon discharge.
- Medication and adverse event review will be performed prior to discharge.
- Complications including vascular, stroke, heart failure etc, and presence of ventricular arrhythmias will be documented.
- NIH stroke scale will be repeat post-procedure
- ICD programming: (see below section 9.2.3)

- The total number of episodes of VT, ATP, and Shocks will be documented at all visits.
- The follow-up includes:
  - 1 Months
    - History and Physical
    - ICD interrogation (may be trans-telephonic)
    - Office BP measurements (x2) including orthostatics
    - Review of Medications and Adverse events
  - 6 Months
    - ICD interrogation (may be trans-telephonic)
    - Review of Medications and Adverse Events
    - Repeat Renal Ultrasound or MR/CT Angiography
  - $\circ$  12 Months:
    - ICD interrogation (may be trans-telephonic)
    - EKG
    - Office BP measurements (x2) including orthostatics
    - Lab tests (CBC, Electrolytes, BUN/Cr)
    - Blood for Renal Hormones (OPTIONAL)
    - BNP Level.
    - Review of Medications and Adverse Events
    - Repeat TTE
  - 18 Months:
    - ICD interrogation (may be trans-telephonic)
    - Review of Medications and Adverse Events
  - o 24 Months:
    - ICD interrogation (may be trans-telephonic)
    - Lab tests (CBC, Electrolytes, BUN/Cr)
    - BNP Level
    - Review of Medications and Adverse Events

#### 9.2.2 POST-PROCEDURE MEDICATION MANAGEMENT

- Standard cardiovascular medications are left up to the discretion of the investigator but BBLs, ACEI, ARBs and aldosterone antagonist use is recommended as per standard guidelines.
- Therapeutic anticoagulation (example Warfarin or equivalent agent) beyond the requisite 1 week post-procedure timepoint is at the discretion of the patient's physician.

### 9.2.3 ICD PROGRAMMING

The following programmed detection and therapy parameters should be used to optimize therapy delivered to the subject during the course of the study for both the Catheter Ablation Group (Treatment) and Control Group:

ICD Frogramming Requirements				
Arrhythmia	ia Programming Strategy			
VT Zone	175-195 bpm			
VF Zone	200 bpm. ATP to 250 bpm			
Monitor Zone	130-170 bpm			
VT Therapy	ATP – recommended. Programmed at investigators discretion			

# ICD Programming Requirements

SVT	Should be -ON" in VT zone.
Discriminators	Programmed at investigators
	discretion.

Arrhythmia	Medtronic	Boston-Scientific	St. Jude	Biotronik
VF	18/24 beats	5s (1-25s std, but	18 intervals (uses	18/24
		would be	binned counter)	
		approx.3-10		
		beats)		
VT	18-20 beats	5s	18-20	18-20 (must be
				VF)
Monitor	No effect (on		Monitor may	
	newer devices)		affect detection	
Comments				Uses the same
				criteria for
				detection and
				redetection

#### **Device Specific Detection Parameters**

#### 9.2 SAFETY

We anticipate no significant increase in adverse events as compared to the VT ablation or renal angiography procedure. The local site primary investigator will oversee the safety of the study at his/her site. All adverse events will be reported to the Data Coordinating Center (Mount Sinai School of Medicine). Adverse events will be monitored and tallied for each 50 patients enrolled in the study (after the 20 patients enrolled during the PILOT phase), and presented to an independent Cardiologist (who will serve as the Data Safety Monitoring individual). All adverse events will be adjudicated as being either: 1) related to the renal denervation procedure; 2) related to the VT ablation procedure or 3) unrelated to either procedure. Because of the small size of this study, the DSMB will consist of one Cardiologist; the PI will also be present at the meetings to relate any pertinent trial information. However, recommendations are solely up to the discretion of the DSMB

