Control Group:	Subjects in the control group will undergo a standard procedure for catheter-based VT ablation.				
Primary Endpoint:	
 
Time to first event requiring appropriate ICD therapy for ventricular arrhythmia or Incessant VT (VT occurring below the ICD rate cut-off)
 
				
Secondary Endpoints:	
 
Appropriate ICD therapy for ventricular arrhythmia
 
Appropriate ICD Shocks ventricular arrhythmia
 
Inappropriate ICD therapy
 
All ICD therapy (Appropriate + Inappropriate)
 
A composite of Mortality, ICD storm, and Incessant VT (VT occurring below the ICD rate cut-off)
 
Number of Hospitalizations for Cardiovascular Causes.
 
Total VT burden (Number of episodes).
 
All-Cause Mortality.
 
The occurrence of ICD storm, defined as ≥3 appropriate shock therapies within 24 hours.
 
Differences in blood hormone measurements (including norepinephrine, aldosterone, renin, and BNP).
 
Differences in Cardiac parameters, including LV size (septal and free wall thickness) and mitral inflow (E&A velocity), as measured by trans-thoracic echocardiography.
 
Procedure related adverse events including, but not limited to hematomas, pseudoanuerysms, renal artery stenosis, renal impairment, thromboembolic events, stroke, pericardial bleeding including tamponade and myocardial infarction
 
Change in blood pressure
 
				

	
 
15. Development of orthostatic hypotension
 
16. Other individual complication rates including, but not limited to MI and death.
 
17. 30-day Major Complication Rate defined as death, stroke, MI or any other serious adverse events related to the treatment or procedure within the first 30 days or through hospital discharge (whichever is longer);
 
18. Procedure time
 

Primary Analytical Analysis:	Intent to treat analysis
Secondary Analytical Analysis:	Per protocol analysis
Principal Investigator:	[name]. Mount Sinai School of Medicine [name]
Site, Monitoring, and Data Management Center	Electrophysiology Clinical Research Group Mount Sinai School of Medicine [name]
Data Safety and Monitoring Board:	TBD

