# 7. Sample Size Calculation:

We generated our sample size using the following key assumptions:

- 1. In patients receiving catheter ablation for VT alone, the estimated success rate (absence of ICD therapy) at 2 years is 65%
- 2. In patients receiving RSDN in addition to VT ablation, we expect a 30% improvement such that the estimated 2 year success rate is 85%

The power analysis revealed that a 30% improvement in therapy with RSDN would be detected with 83 patients per arm (80% power, 2-sided alpha error of 0.05). This would require an enrollment of a total of 168 patients, with follow-up of 2 years. We expect an ~10% loss to follow-up. Accordingly, we will plan to enroll an additional ~10% of patients so as to have sufficient number of randomized patients: this would require 184 patients. In addition, we expect 10% of patients will have renal vasculature inappropriate for the RSDN procedure (these are patients that will be consented pre-procedure, but will screen out after renal angiography during the VT ablation procedure). Accordingly, we will ultimately plan to include a total of 202 patients: ~18 patients would screen out after renal angiography, and there would remain a total of 92 patients randomized to each arm.

This study is divided into two phases: a PILOT phase (to include 20 patients) followed by the remaining 182 patients to a total of 202 patients. The PILOT phase will be conducted at 2 sites: Homolka Hospital (Prague, Czech Republic) and Mount Sinai Medical Center. An interim safety

[figure not shown]
analysis for the primary endpoint will be conducted when all patients in the PILOT phase (20 subjects) have completed the 1-month follow up visit.

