### 9. Pre-Procedure and Ablation Study Design Flow-Chart

#### **PRE- AND ABLATION PROCEDURE**

### 9.1.1 **PRE-PROCEDURE**

The following tests and procedures will occur before the ablation:

- Recording of patient medical history (including details of VT both clinical/ICD)
- Recording medication history (including all AAD ever used, duration of use)
- Obtain β-HCG in females of child bearing age the morning of the procedure as per usual clinical practice
- Baseline assessment of arrhythmia burden and type: Office/inpatient records, ICD interrogation report
- Baseline NIH stroke scale
- If performed for any reason, collect any pre-procedural imaging: MRI/CT and Renal Ultrasounds within 6 months of procedure
- Baseline laboratory, including complete blood count, standard electrolyte panel, renal function, and brain natriuretic peptide levels.
- Baseline Transthoracic Echocardiogram
- Baseline blood pressure. Proper blood pressure measurement technique is essential: i) patient should sit quietly in a chair with his/her back supported for 5 minutes before taking the measurement; ii) use of the correct cuff size with the air bladder encircling at least 80% of the arm (the adult large cuff for the majority of patients); iii) support the arm at heart level during the cuff measurement; iv) a minimum of 2 readings should be taken at intervals of at least 1 minute and the average of those readings should be taken to represent the patient's blood pressure; v) the blood pressure should be measured
- Consent must be obtained before the VT ablation procedure.
- Randomization into one of two groups will be performed by opening the Randomization envelope after Renal Angiography.

Study/Experimental Group: These subjects will undergo catheter-based sympathetic renal denervation.

Placebo Control Group: These subjects will receive no further intervention..

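### Every patient has renal angiography before randomisation, but the adverse-event attribution has no correct label for its harms, so attributed tallies can be wrong and can differ by arm

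*Combined protocol and SAP*

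**What the plan says.** Section 9.1.4 sets the exposure: "Abdominal aortography will be performed to assess the renal arteries for the suitability of catheter-based renal denervation in all patients". Section 9.1.1 sets the order: "Randomization into one of two groups will be performed by opening the Randomization envelope after Renal Angiography". Section 7 places the angiogram in the same session as the ablation, describing consented patients who "screen out after renal angiography during the VT ablation procedure".

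The Control Group entry of the Protocol Summary does not mention it: "Subjects in the control group will undergo a standard procedure for catheter-based VT ablation". The opening of 9.3 Risks likewise starts from a standard VT ablation. It lists the risks of that procedure and then the additional risks of RSDN, with no list for angiography.

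Section 9.2 Safety treats angiography as a procedure with adverse events of its own: "We anticipate no significant increase in adverse events as compared to the VT ablation or renal angiography procedure". The same paragraph then fixes the attribution rule: "All adverse events will be adjudicated as being either: 1) related to the renal denervation procedure; 2) related to the VT ablation procedure". The list closes with "2) related to the VT ablation procedure or 3) unrelated to either procedure". The tallies go to a single independent cardiologist.

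Two other rules depend on whether an event counts as procedure-related, and neither defines the term. They are secondary endpoint 13 in section 5.2, and the rule in 9.3.1 that ends the trial if more than 15% of the treatment arm has a severe event of that kind.

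**The concern.** Take a control patient, or one who screens out, whose renal function falls because of the angiogram. The first category is impossible, since no denervation was done. The second blames the VT ablation. The third calls harm from a protocol-mandated step unrelated. None names the cause.

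In the RSDN arm the same injury can be filed under denervation. The operator knows the allocation, and the independent committee in 9.3.2 is charged with ICD events only, so nothing in the text prevents the same event from being labelled differently by arm. At stake are the attributed tallies shown to the safety cardiologist, and the trial's ability to report what the angiogram itself costs patients.

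**Working it through.** **Patient flow (section 7).** 202 enrolled − 18 screened out after angiography = 184 = 2 × 92 randomised. The plan's own figures reproduce.

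**Exposure to angiography without RSDN.** 92 controls + 18 screen failures = 110; 110 / 202 = 54%.

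**Expected angiography harms.** The documents give no complication rate *r*, so it is an assumption, taken over 0.5% to 5%. Expected events = headcount × *r*.

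| Assumed *r* | 92 controls | 18 screen failures | 110 without RSDN | 92 RSDN | All 202 |
|---|---|---|---|---|---|
| 0.5% | 0.46 | 0.09 | 0.55 | 0.46 | 1.01 |
| 1% | 0.92 | 0.18 | 1.10 | 0.92 | 2.02 |
| 2% | 1.84 | 0.36 | 2.20 | 1.84 | 4.04 |
| 5% | 4.6 | 0.9 | 5.5 | 4.6 | 10.1 |

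**Comparison of all events, ignoring attribution.** Both arms have the angiogram before allocation, so its expected contribution to the difference is 92*r* − 92*r* = 0 for every *r*, however events are coded.

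**Comparison of attributed events.** This depends on the coding:

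- Filed as RSDN in the RSDN arm and as VT ablation or unrelated in controls: the RSDN-attributed count rises by up to 92*r*, that is 0.46 to 4.6 events, and this does not cancel.
- Filed as VT ablation in both arms: the VT ablation count is too high by 92*r* in each arm, and angiography harm is invisible.
- Filed as unrelated in both arms: these events drop out of any procedure-related count that is built on the attribution.
- In every case the 18 screen failures (0.09 to 0.9 expected events) belong to neither arm.

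**Sensitivity of the 15% rule.** With 10 RSDN patients in the pilot, 15% is 1.5 patients: 1/10 = 10% is below the limit and 2/10 = 20% is above it. The coding of one severe angiography event could therefore decide whether the limit is passed. With 92 patients it is 0.15 × 92 = 13.8, so the 14th patient passes it.

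**The case against.** The strongest reply is that nothing is lost. All adverse events are reported. Secondary endpoints 13, 16 and 17 count complications without using the three categories, 6-month renal imaging is scheduled without restriction by arm, and section 9.1.4 already has screen failures assessed for procedure-related events. Because the angiogram is done within the ablation session, the VT ablation category can be read to include it. The angiogram is also plainly disclosed: the Protocol Summary makes it the test of eligibility, and later sections repeat this. Giving it to both arms is proper design, since it isolates the effect of denervation.

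Most of this stands. The events are mislabelled, not missing, and the randomised contrast is sound for its purpose. It does not remove the point. Reading angiography into the VT ablation category conflicts with 9.2 itself, which names the two separately. And because the randomised contrast cannot show angiography harm, attribution is the only way the trial can report it, which is where the category is absent.

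Two stronger readings are tempting but unsupported. A reader might infer that the attribution scheme makes angiography harm cancel between arms. The cancellation comes from both arms having the procedure, and a fourth category would not alter it. A reader might also infer from the list in 9.3 that renal artery dissection and stenosis are recognised only as RSDN risks. Section 11.1 gives both as possible risks without that limit, and secondary endpoint 13 lists stenosis without restriction by arm.

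**Conclusion.** The attribution rule in 9.2 is faulty as written. It recognises renal angiography as a procedure and then gives its harms no correct label. This affects 110 of 202 patients (54%) who have the angiogram without RSDN, and it allows labels in the RSDN arm to differ from those in controls. At an assumed 0.5% to 5% complication rate, about 0.6 to 5.5 events among the 110 would be mislabelled. That range is only as good as the assumed rate.

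A reader might go further and say the trial understates the excess harm of RSDN by a few percentage points. The documents do not support this. Such a figure merely returns the assumed rate, and it refers to VT ablation without an angiogram, a comparison the trial does not make. Arm-dependent filing would in fact raise the RSDN-attributed count.

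That the angiogram is done only for the trial is inferred from its stated purpose; the text does not say so outright. Nothing is concluded about what participants are told, since the consent form is not available. The defect concerns safety reporting and does not invalidate the randomised comparison.

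**What to change.** 1. In 9.2 Safety, add a fourth attribution category, *related to renal angiography/aortography*, applied identically to both arms and to screen failures.
2. Tabulate those events descriptively for everyone who had an angiogram (about 202 patients), beside the randomised comparison and not in place of it.
3. State whether such events count as procedure-related in secondary endpoint 13 and in the 15% rule of 9.3.1, so that the two are read alike.
4. Amend the Control Group entry of the Protocol Summary and the opening of 9.3 Risks to say that controls receive VT ablation plus renal angiography.

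The cost is one more option for the adjudicator, one more table and a few lines of wording. It needs no new procedure, visit or patient, because adverse events in screen failures are already to be assessed under 9.1.4.

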#### 9.3.1 Interim and Futility Analyses

An interim or futility analyses will be performed after completion of the PILOT phase of this study: after the enrollment of 20 subjects (10 controls, 10 study group). This analysis will be presented to the DSMB, who has the authority to terminate the study prematurely if an increase in adverse events is encountered. If the DSMB determines the trial should be stopped early either because of efficacy or safety concerns, or otherwise modified, the DSMB will prepare formal written recommendations to the PI to consider final action. Moreover, any pressing safety concerns that the DSMB identifies will be verbally communicated to the PI as soon as possible, prior to written documentation. The trial will be terminated early if severe procedure-related adverse events occur in more than 15% of patients in the treatment arm.

#### 9.3.2 Clinical Events Committee

A separate Clinical Events Committee (CEC) composed of 2 independent electrophysiologists will adjudicate all ICD events in this study.

### 9.3 RISKS

VT ablation will occur according to standard procedure, and therefore the risk includes that of a standard VT ablation. These risks include:

### Common:

- Discomfort at the site of vascular access
- Groin hematoma

#### **Uncommon:**

- Bleeding
- Vascular injury
- Thromboembolism, including renal infarction and peripheral atheroembolism. This risk is minimized considerably by the short duration of the procedure, as well as the use of a saline-irrigated ablation catheter.
- Risks associated with sedatives/anesthesia.
- Injury to adjacent structures (phrenic nerve, cardiac valves)
- Vascular complications (including pseudoaneurysm, AV fistula requiring surgical intervention)
- Radiation burns
- Pneumonia and/or sepsis
- Death
- Discomfort in the throat region
- Cardiac Perforation requiring drainage or surgery
- Injury to adjacent structures (phrenic nerve, esophagus, lung, cardiac valves)
- Congestive heart failure
- Myocardial infarction
- Radiation burns

The potential additional risks of the RSDN procedure are anticipated to be uncommon but may include:

- Renal artery dissection
- Renal artery stenosis or occlusion
- Renal dysfunction potentially needing hemodialysis
- Thromboembolism, including renal infarction and peripheral atheroembolism. This risk is minimized considerably by the short duration of the procedure, as well as the use of a saline-irrigated ablation catheter.

### **10.0 STUDY MANAGEMENT**

### **10.1 Study Data Collection and Processing**

The Case Report Form (CRF) is an integral part of the study and subsequent reports. The CRF must be used to capture all study data recorded in the patient's medical record. The CRF must be kept current to reflect patient status during the course of the study. Patients will be identified by a 5 digit number and their initials. The investigator must keep a separate log of patient names and medical record numbers (or other personal identifiers) for their own reference. All study-related documents (CRFs, source medical records, regulatory binder must be kept in a secure, locked environment with access limited to study personnel only.

The PI is responsible for ensuring the following at his/her site: 1) adherence to the protocol; 2) verifying adherence to local regulations on the conduct of clinical research; and 3) ensuring completeness, accuracy, and consistency of the data entered in the CRF. Final CRFs in human readable format must be reviewed and verified for accuracy by the study site Principal Investigator and signed-off. A copy of the final CRF will remain at the investigator's site at the completion of the study.

The CRF numbering convention is as follows:

\_\_01\_-2\_\_3\_4\_A-B-A \_\_01\_: Site # must be 2 digits (use leading zero) --- (sites 01-10)

 $2_3_4$ : patient screening/enrollment # (001 – 500)—must be 3 digits

A-B-A: Patient initials (if no middle initial, use dash) Total 5 digits and initials for enrolled patients.

